7.1.2 Screening

Screening assessments to confirm eligibility should be performed as per the schedule of assessments. Written informed consent must be obtained before any study specific procedure is performed.

Re-screening of patients will not be allowed, but laboratory parameters which do not meet the inclusion criteria may be re-tested within the 28 day screening window.

7.1.2.1 Eligibility screening

Following registering in the IRT for screening, patient eligibility will be checked once all screening procedures are completed. The eligibility check will be embedded in the IRT system. Please refer to and comply with the detailed guidelines in the IRT manual.

7.1.2.2 Information to be collected on screening failures

Patients who sign an informed consent but fail to be started on treatment for any reason will be considered a screening failure.

The following eCRFs must be completed for screening failure patients:

- Screening Phase Disposition page (including reason for not being started on treatment)
- Informed consent
- Demography
- Adverse Events (only if an SAE occurs)
- Inclusion/Exclusion criteria

7.1.2.3 Patient demographics and other baseline characteristics

Data to be collected on patient characteristics at screening include:

- Demography (including: date of birth, age, patient initials, gender, childbearing potential, race and ethnicity, or as allowed by local regulations)
- Relevant medical history
- NSCLC diagnosis and extent of disease, including:
 - Date of diagnosis and stage of NSCLC
 - ALK status documentation using the FDA-approved Vysis ALK break-apart FISH assay. ALK status must be confirmed using the FDA-approved Vysis ALK break-apart FISH test via a central laboratory using the new biopsy obtained prior to study entry (if biopsy was taken) or, if a new biopsy is not available, using the required archival tumor tissue.
 - Site of active disease
 - Characteristics of disease
- Prior antineoplastic therapies (medications, radiation, surgeries)
- Prior and Concomitant Medications, surgical and medical procedures

All other medications taken within 28 days before the first dose of study treatment is administered must be recorded on the Prior and Concomitant medication eCRF page and updated on a continual basis if there is new change to the medication.

7.1.3 Treatment period

The study treatment phase begins on Cycle 1, Day 1 with the first administration of LDK378 and will continue until unacceptable toxicity that precludes further treatment, start of a new anti-cancer therapy, treatment is discontinued at the discretion of the investigator and/or patient death. If a patient experiences disease progression (radiologically documented according to RECIST 1.1 as assessed by the investigator), LDK378 administration may be stopped, or may be continued if the patient is continuing to derive clinical benefit in the opinion of the investigator (see [Section 6.1.3](#)).

Patients will be assessed as per visit schedule in [Table 7-1](#).

Visit windows of ± 1 calendar day will be applicable to scheduled study assessments during Cycle 1. Visit windows of ± 3 days from scheduled study assessments will apply during and beyond Cycle 2. The only exception is imaging assessments, which have a 7 day window at all scheduled timepoints.

7.1.4 Discontinuation of study treatment

7.1.4.1 Patients discontinuing LDK378

A patient will be defined as on the study if they are continuing to have any study data collected, i.e. if the patient is being treated with LDK378, is in efficacy follow-up after discontinuing LDK378, or is in survival follow-up.

Patients may voluntarily discontinue from the study treatment for any reason at any time. If a patient decides to discontinue from the study treatment, the investigator must make every effort (e.g. telephone, e-mail, letter) to determine the primary reason for this decision and record this information in the patient's chart and on the appropriate CRF pages. They may be considered withdrawn if they state an intention to withdraw, fail to return for visits, or become lost to follow-up for any other reason.

The investigator should discontinue study treatment for a given patient if, on balance, he/she believes that continuation would be detrimental to the patient's well-being.

Study treatment must be discontinued under the following circumstances:

- Emergence of adverse events, as described in [Section 6.3](#)
- Laboratory abnormalities, as described in [Section 6.3](#)
- Pregnancy
- Deviations from the prescribed dose regimen, as described in [Section 6.2.3](#)
- Use of prohibited treatment, as described in [Appendix 1](#) for LDK378
- Any other protocol deviation that results in a significant risk to the patient's safety
- Study Terminated by Sponsor
- Patient/guardian decision
- Physician decision
- Lost to follow-up
- Death

Patients who discontinue study treatment should NOT be considered withdrawn from the study. They should return for the assessments indicated in [Section 7.2.1](#) and enter the survival follow-up period or continue tumor assessments as appropriate. If they fail to return for these assessments for unknown reasons, every effort (e.g. telephone, email, letter) should be made to contact them as specified in [Section 7.1.6](#).

End of treatment visit

Patients who discontinue LDK378 should be scheduled for a visit as soon as possible and within 7 days of the last dose of LDK378, at which time all of the assessments listed for the EOT visit will be performed. If a patient withdraws from treatment at a study visit, EOT

assessments do not need to be repeated. An End of Treatment Phase Disposition eCRF page should be completed, giving the date and reason for stopping LDK378 treatment. As a minimum, all patients who discontinue LDK378, including those who refuse to return for a final visit, will be contacted for safety evaluations at least 30 days after the last dose of LDK378. The investigator should inquire about any AE observed/concomitant medication taken during this 30-day period. This can be done via a phone contact. Antineoplastic therapies will be captured on the 'Antineoplastic therapies since discontinuation of study treatment' eCRF page following the last dose of the LDK378.

7.1.4.2 Withdrawal of consent

[REDACTED]

7.1.5 Follow-up period

7.1.5.1 Post-treatment efficacy follow-up

If a patient discontinues study treatment in the absence of confirmed PD, tumor assessments every 8 weeks should continue to be performed from the EOT visit until PD is assessed by the investigator (see [Section 7.2.1.2](#)); however, safety assessments do not need to continue to be performed. Antineoplastic therapies since discontinuation of study treatment will continue to be collected.

Once the patient ceases tumor follow-up, the reason for completion should be recorded on the Study Phase Completion Disposition eCRF page.

7.1.5.2 Survival follow-up

Following the end of tumor follow-up for efficacy (i.e. after the time of confirmed PD), the patient will be contacted every 3 months to determine survival status and antineoplastic therapies since discontinuation of study treatment.

7.1.6 Lost to follow-up

For patients whose status is unclear because they fail to appear for study visits without stating an intention to withdraw consent, the investigator should show "due diligence" by contacting

[REDACTED]

the patient, family or family physician as agreed in the informed consent and by documenting in the source documents steps taken to contact the patient, e.g. dates of telephone calls, registered letters, etc. A patient should not be considered lost to follow-up until due diligence has been completed. Patients lost to follow up should be recorded as such on the appropriate Disposition CRF.

7.2 Assessment types

7.2.1 Efficacy assessments

Tumor evaluation will be determined locally according to the Novartis guideline ([Appendix II](#)) on the Response Evaluation Criteria in Solid Tumors (RECIST), based on RECIST Version 1.1 ([Eisenhauer et al 2009](#)). The investigator's assessment will be used for the primary endpoint analysis and for patient's treatment decision making.

Imaging data will be centrally collected and checked for quality by an imaging Clinical Research Organization (CRO) designated by Novartis. It will undergo review by a blinded independent review committee (BIRC) according to the Novartis guideline ([Appendix II](#)) on the Response Evaluation Criteria in Solid Tumors (RECIST), based on RECIST Version 1.1.

Full details of the central reading process are included in the BIRC Charter.

7.2.1.1 Baseline assessments

Details of imaging requirements and logistics can be found in the separate Imaging Manual.

Tumor evaluation will be performed at baseline within 28 days of, and prior to, enrollment. Contrast-enhanced CT (or MRI) should preferably be performed using a 5 mm slice thickness with a contiguous reconstruction algorithm. CT/MRI scan slice thickness should not exceed 8 mm cuts using a contiguous reconstruction algorithm.

Required conditions for tumor assessment at baseline

- Patients must have measurable disease as per RECIST 1.1 ([Appendix II](#)). Measurable lesions include lytic or mixed (lytic + blastic) bone lesions with an identifiable soft tissue component that meets the measurability criteria per RECIST 1.1 ([Appendix II](#)).
- Patients with only non-measurable lesions are not eligible.
- If the measurable disease is restricted to a solitary lesion, its neoplastic nature should be confirmed by cytology/histology.
- Any potentially measurable lesion that has been previously treated with radiotherapy should be considered as a non-measurable lesion. However, if a lesion previously treated with radiotherapy has clearly progressed since the radiotherapy, it can be considered as a measurable lesion.
- All measurable lesions up to a maximum of 5 nodal and/or non-nodal lesions in total (and a maximum of 2 lesions per organ), representative of all involved organs, should be identified as target lesions and recorded and measured at baseline.

Required image assessments for tumor assessment at baseline

The following assessments will be performed:

- Computed Tomography (CT) with IV contrast or Magnetic Resonance Imaging (MRI) of chest and upper abdomen.
 - The preferred radiologic technique is CT with intravenous (IV) contrast. If a patient is known to have a contraindication to CT contrast media or develops a contraindication during the trial, a non-contrast CT of the chest (MRI is not recommended due to respiratory artifacts) plus a contrast-enhanced MRI (if possible) of the upper abdomen should be performed.
- A whole body bone scan according to institutional guidelines (e.g. Tc-99 bone scan, whole body bone MRI, FDG-PET or sodium fluoride positron emission tomography (NaF PET)).
 - After screening, scans need not be repeated, unless clinically indicated. If indicated, the same methodology as at screening should be used.
- Localized CT, MRI or X-rays of all skeletal lesions identified on the screening bone scan, which are not visible on the chest and abdomen CT/MRI (and pelvis CT/MRI if applicable).
 - After screening, scans need not be repeated, unless clinically indicated. If indicated, the same methodology as at screening should be used.
- Brain CT with IV contrast or MRI scan.
 - After screening, scans need not be repeated, unless clinically indicated. If indicated, the same methodology as at screening should be used.
- Color photographs (with a metric ruler) if skin lesions are present.
 - After screening, scans need not be repeated, unless clinically indicated. If indicated, the same methodology as at screening should be used.
- CT or MRI of any other site of disease not captured by any of the above listed images (e.g., pelvis, neck).
 - After screening, scans need not be repeated, unless clinically indicated. If indicated, the same methodology as at screening should be used.

Any imaging assessments already completed during the regular work-up of the patient within 6 weeks prior to start of treatment, including before signing the main study ICF, can be considered as the baseline images for this study.

Chest x-ray or ultrasound must not be used to measure tumor lesions.

7.2.1.2 Subsequent image assessments for response determination

Tumor assessment for response determination will be made every 8 weeks starting from Day 1 of cycle 1 (+/- 7 days window). **The 8 weeks interval should be respected regardless of whether treatment with LDK378 is temporarily withheld.**

Post-baseline tumor assessments

The following assessments will be performed at on-study scheduled visits (see [Table 7-1](#)):

- Computed Tomography (CT) or Magnetic Resonance Imaging (MRI) of chest and upper abdomen.
- Localized CT, MRI or X-rays of all skeletal lesions identified on the screening bone scan, which are not visible on the chest and upper abdomen CT/MRI (and pelvis CT/MRI if applicable). Whole body bone scans need not be repeated after baseline unless clinically indicated.
- Brain CT with IV contrast or MRI, if brain metastases were identified at baseline.
- Color photographs (with a metric ruler) if skin lesions were documented at baseline.
- CT or MRI of any other site of disease documented at baseline (e.g., pelvis, neck).

For post-baseline tumor assessments, all lesions that were present at baseline must be accounted for using the same technique as used at baseline so that the comparison is consistent. If possible, a single radiologist should perform all tumor response evaluations for an individual patient.

All study imaging performed, including any intercurrent imaging studies, whether or not suspected to fulfill a progression or response criterion, should be submitted to the designated imaging CRO for quality control and the BIRC review promptly after acquisition. The activities of the imaging CRO and the BIRC will be described in the Imaging Charter.

Criteria required for determining partial or complete response should be confirmed by a subsequent imaging assessment at least 4 weeks later. If an off-schedule imaging assessment is performed to confirm response or if progression is suspected, subsequent imaging assessments should be performed in accordance with the original imaging schedule unless the next scheduled imaging timepoint is within 2 weeks, in which case the scheduled imaging timepoint can be omitted.

Combined PET/CT may be used only if the CT is of similar diagnostic quality as a CT performed without PET, including the utilization of oral and IV contrast media. At the discretion of the Investigators, FDG-PET scans may be performed to document progressive disease per RECIST 1.1 ([Appendix II](#)).

Imaging evaluations will be performed at the End of Treatment (EOT) visit. If a patient is known to have PD at a scheduled study visit, EOT imaging evaluations do not need to be repeated for the EOT visit.

Imaging assessment by the BIRC

All radiological assessments will be read locally and should be submitted promptly after acquisition to the imaging CRO designated by Novartis. The process at the imaging CRO will ensure that the BIRC remains blinded to the results of the local assessment (and other unblinding information). The decision regarding patient management will remain with the local investigator.

Rapid image transmission to the BIRC may be accomplished by uploading all digital images acquired by the investigator in a secured website.

The results of the BIRC assessment will not be communicated to sites.

All timepoints will be read on an ongoing basis (rolling reads) as detailed in the imaging charter to be provided by the designated imaging CRO.

Duration of post-baseline tumor assessments

Tumor assessments will continue until one of the following events:

- The patient experiences RECIST-defined PD as determined by the investigator AND treatment with LDK378 ceases. If treatment with LDK378 continues beyond RECIST-defined PD, imaging assessments must continue every 8 weeks until LDK378 treatment ceases
- If a patient discontinues study treatment in the absence of PD, tumor assessments will continue to be performed every 8 weeks until the patient experiences a RECIST-defined PD as determined by the investigator
- Death
- Lost to follow-up, or
- Patient decision involving withdrawal of consent (see [Section 7.1.4.1](#)).

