## 2.8 Analysis of secondary variables

### 2.8.1 Efficacy

All tumor response related endpoints under the secondary efficacy objectives (DOR, TTR, DCR, PFS) will be analyzed as per investigator assessment and as per the BIRC. Confirmation of response is required for all response endpoints, as per RECIST 1.1.

All secondary endpoint analyses will be performed based on the FAS, unless otherwise specified.

No adjustment for multiple testing will be made.

The key secondary efficacy endpoints are

- ORR by BIRC
- DOR by investigator assessment and by BIRC
- DCR by investigator assessment and by BIRC
- TTR by investigator assessment and by BIRC

Other secondary efficacy endpoints are

- PFS by investigator assessment and by BIRC
- OS

The definitions and details on the derivation of the secondary endpoints are given in the LDK378A2203 protocol. Further details and notes needed for programmatic implementation of RECIST 1.1 guidelines are provided in [Section 4.6.1](#).

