## Duration of response

Among patients with a confirmed response (PR or CR), DOR is defined as the time from first documented response (PR or CR) to the date of first documented PD or death due to underlying cancer. If a patient has not had an event, DOR is censored at the date of last adequate tumor assessment.

The censoring and event date options to be considered for the main analysis are presented in [Table 2-1](#).

Table 2-1 Outcome and event dates for DOR and PFS analyses

	Situation	Date	Outcome
A	No baseline assessment	Date of first dose of study drug*	Censored
B	Progression at or before next scheduled Assessment	Date of progression	Progressed
C1	Progression or death after exactly one missing assessment	Date of progression (or death)	Progressed
C2	Progression or death after two or more missing assessments	Date of last adequate assessment†	Censored
D	No progression	Date of last adequate assessment •	Censored
E	Treatment discontinuation due to 'Disease progression' without documented progression, i.e. clinical progression based on investigator claim	N/A	Information ignored. Outcome derived based on radiology data only.
F	New anticancer therapy given	Date of last adequate assessment •	Censored
G	Deaths due to reason other than deterioration of 'Study indication'	Date of last adequate assessment •	Censored (only applicable to DOR)

• The rare exception to this is if the patient dies no later than the time of the second scheduled assessment as defined in the protocol in which case this is a PFS event at the date of death

• After the last adequate tumor assessment. "Date of next scheduled assessment" is defined in Section 3.2.7 of Section 14 (Appendix II) of the LDK378A2203 protocol

DOR will be described in tabular and graphical format using Kaplan-Meier methods including estimated median (in months) with 95% CI, 25th and 75th percentiles (Brookmeyer and Crowley 1982, Klein and Moeschberger 2005) and Kaplan-Meier estimated probabilities with confidence intervals (Kalbfleisch and Prentice 2002) at several time points (including at least 4, 8, 12, 15, 18 months).

These analyses will be performed separately based on investigator assessment and based on BIRC assessment.

Refer to Section 4.6.3 for further details regarding derivation of Kaplan - Meier estimates.

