1. Ongoing
2. New cancer therapy
3. Withdrew consent
4. Loss to follow-up

However, if this distance is larger than D2, then the censoring reason will be 'Adequate assessment no longer available'.

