**Table 4-3 Sources for overall lesion response**

Source 1	Investigator (local radiology) reported overall lesion response
Source 2	Calculated overall lesion response based on raw (i.e. individual lesion) measurements from Investigator (local radiology)
Source 3	BIRC (Blinded Independent review committee) reported overall lesion response

In this study, Source 1 will be used for the primary endpoint derivation and other secondary endpoint calculations based on investigator assessment (ORR, DCR, DOR, TTR and PFS) and Source 2 will be listed against Source 1 and discrepancies between calculated and reported responses assigned by investigator will be identified. Source 3 will be used to calculate ORR, DCR, DOR, TTR and PFS by BIRC.

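### Imaging ends at investigator PD once LDK378 has stopped, without waiting for BIRC PD, so BIRC PFS and DOR are open to plausibly informative censoring that the visible SAP does not count or bound

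*Protocol*

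**What the plan says.** **When imaging ends.** Protocol section 7.2.1.2 (Duration of post-baseline tumor assessments), in line with section 4.1, stops scans when "The patient experiences RECIST-defined PD as determined by the investigator AND treatment with LDK378 ceases". For patients kept on drug after PD, "imaging assessments must continue every 8 weeks until LDK378 treatment ceases". For those who leave treatment without PD, "tumor assessments will continue to be performed every 8 weeks until the patient experiences a RECIST-defined PD as determined by the investigator". Every trigger is the investigator's call.

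**What the BIRC does.** It reads all images blinded to the local result, and "The results of the BIRC assessment will not be communicated to sites".

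**What is analysed.** SAP section 2.8.1 states that DOR, TTR, DCR and PFS "will be analyzed as per investigator assessment and as per the BIRC". SAP section 4.6.2 adds: "Source 3 will be used to calculate ORR, DCR, DOR, TTR and PFS by BIRC".

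**How non-events are handled.** In SAP Table 2-1, row D censors a patient without progression at the last adequate assessment. Row F ("New anticancer therapy given") censors at the same point. Row C2 censors a progression or death that follows two or more missing assessments. For DOR only, row G also censors deaths not due to the study indication.

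**What is reported about censoring.** SAP section 4.6.1 lists four PFS reasons: ongoing, new therapy, consent withdrawn and loss to follow-up. It then gives a residual one: "However, if this distance is larger than D2, then the censoring reason will be 'Adequate assessment no longer available". The PFS text in section 2.8.1 says censoring reasons will be summarised; the DOR text does not.

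**The concern.** Take a patient whose scan the investigator reads as PD and the BIRC reads as SD, PR or CR. If LDK378 stops, the schedule asks for no further scan, and the site cannot know that the BIRC is still waiting for one. In the BIRC analysis this patient leaves the risk set at that scan.

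Kaplan-Meier assumes that censored patients have the same outlook as those still followed. Here the exit was triggered by a reader judging that the tumour had grown, so these patients may well be closer than average to BIRC progression. If they are, BIRC PFS and DOR come out too high.

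DOR by BIRC is a key secondary endpoint and PFS by BIRC another secondary endpoint. In an open-label single-arm trial the BIRC supplies the independent reading. A gap between BIRC and investigator curves could be real reader difference or this artefact, and nothing in the visible SAP separates the two.

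**Working it through.** **1. The plan's own figures.** SAP section 4.6.1 sets D2 = (2 × 8) + 2 = 18 weeks, which reproduces. A death within 18 weeks of the last adequate scan, without new therapy, is therefore a PFS event; a later one is censored. Protocol Table 10-1 also reproduces from exact binomials (type I error 0.0487 against 0.049, power 0.9000 against 0.900). It rests on investigator ORR, so this issue does not touch it. The documents give no figure for the bias itself.

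**2. Tracing the patient.** Investigator PD, drug stopped, no BIRC PD: no later scheduled scan (Protocol 7.2.1.2); no Source 3 event (SAP 4.6.2); censored under row D, or row F if new therapy starts. At the 22-Jan-2018 cut-off, the PFS label would usually be new therapy or the residual category, pooled with patients censored for other causes.

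**3. An illustrative size for 12-month PFS.**
- From the documents: scans every 8 weeks, i.e. 56/30.4375 = 1.84 months, so 6 scans by month 12. Illustrative medians of 6.7 months (phase I, ALK-inhibitor-pretreated) and 7.7 months (crizotinib, second line) come from Protocol section 1.3.
- Assumed: medians of 12 and 18 months; exponential time to BIRC PD; in a share d of patients the investigator calls PD one scan before the BIRC would; a share s = 0.7 of those stop drug and imaging; no deaths.

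Let h = 1 − 2^(−1.84/median) be the risk of BIRC PD per scan interval, and c = d × s. True 12-month PFS is (1 − h)^6. From the second scan on, the observed hazard is h(1 − c)/(1 − ch), so observed PFS = true PFS × (1 − ch)^(−5).

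| Median (months) | h | True | d = 10% (c = 0.07) | d = 20% (c = 0.14) | d = 30% (c = 0.21) |
|---|---|---|---|---|---|
| 6.7 | 0.173 | 0.319 | 0.339 | 0.361 | 0.384 |
| 7.7 | 0.153 | 0.370 | 0.391 | 0.412 | 0.436 |
| 12 | 0.101 | 0.529 | 0.548 | 0.567 | 0.588 |
| 18 | 0.068 | 0.654 | 0.670 | 0.686 | 0.703 |

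The rise is about 2 points at 10%, 3 to 4 at 20% and 5 to 7 at 30%. A simulation of 200,000 patients per scenario agrees with the formula: at median 7.7, c = 0.30, it gives 0.468, and the formula gives 0.370 × (1 − 0.30 × 0.1526)^(−5) = 0.468.

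**4. What moves the answer (simulation).**
- If every discordant patient stops drug (s = 1), the rise is 2.3 to 9.8 points; if half stop (s = 0.5), 1.1 to 4.5.
- If 30% of those who stop die within 18 weeks and count as events, the s = 1 error falls by about a third, to 1.6 to 6.6.
- If investigator calls are unrelated to BIRC progression risk (5% per scan), the error vanishes: 0.369 against 0.369 at median 7.7.

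**5. How much belongs to row F.** Suppose 80% of those who stop start new therapy before the next scan (assumed). Even with continued imaging, row F would censor c = 0.07 × 0.8 = 0.056. At median 12 and d = 10% the rise would be 1.5 points, against 1.9 with imaging stopped.

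**6. What the sensitivity rule does.** Counting these patients as events at investigator PD gives true PFS × (1 − ch). At median 7.7, c = 0.14: 0.370 × (1 − 0.14 × 0.1526) = 0.362. The main estimate (0.412) and the sensitivity estimate (0.362) then bracket the truth (0.370).

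**The case against.** Much of the opposing case stands, and it limits the point.

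- A reader might infer that scans stop at investigator PD outright. They do not: drug must also have stopped, and patients treated beyond PD stay on the 8-weekly schedule.
- A reader might take upward bias as shown. The documents give neither a discordance rate nor the share stopping drug at PD. The model above also assumes BIRC PD at the very next scan, which is near the worst case.
- A reader might quote medians. In one simulation with 10% discordance, a true median of about 13 months became 14.5, while 12-month PFS moved only from 0.534 to 0.554. The median jump mostly reflects the 1.84-month scan grid.
- A reader might conclude that BIRC results must look better than investigator results. The BIRC may also call PD earlier, so the net gap is unknown.
- A reader might invoke row E or the SAP 4.6.1 text on progression without objective evidence. Those concern undocumented progression; here the investigator's PD is radiological, so only row D or F applies.
- Saying there is no check would go too far. Investigator PFS and DOR are reported alongside, and PFS censoring reasons are tabulated. Protocol Appendix II, the earlier RAP and the imaging charter are not available to inspect.

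What survives is that these checks are partial. The parallel investigator curve cannot say why the two differ, the censoring table pools the affected patients with others, and no DOR censoring table is stated.

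**Conclusion.** The point holds as a likely upward bias of unknown size in BIRC PFS and DOR, with no targeted check in the visible SAP. The mechanism follows from the plan as written; the direction rests on discordance being related to prognosis. Under that assumption, with 10 to 30% discordance and 70% stopping drug at PD, 12-month BIRC PFS is overstated by about 2 to 7 points. Early deaths would reduce this, and part of it belongs to censoring at new therapy rather than to the imaging stop. DOR was not sized. The death allowance is narrower there because row G censors deaths from other causes.

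The documents do not support reading this as a proven bias, as a flaw in the primary analysis, or as grounds to set BIRC results aside. These endpoints are descriptive, and the investigator-ORR test, its alpha and its power are untouched. It is a cheap improvement worth making.

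**What to change.** In SAP section 2.8.1, Table 2-1 and section 4.6.1:

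1. Add a censoring reason for BIRC PFS and BIRC DOR: investigator PD, no BIRC PD, no later BIRC-read scan. Report its count, split by whether new anticancer therapy had started, so that the imaging stop and row F can be told apart.
2. Add one sensitivity analysis each of BIRC PFS and BIRC DOR in which these patients have an event at the investigator PD date. Show medians and landmark rates beside the main BIRC estimates. Label the result a conservative bound, because it borrows the investigator's call and is no longer an independent read. A rule that BIRC results count only if both analyses agree should not be added without an agreement criterion.

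The cost is two extra Kaplan-Meier runs and one extra censoring category, from data already held, with no new scans or reads. The drawback is that the BIRC estimates may look less favourable.
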